- 5. Laboratory or clinical variables: X-rays, serological or microbiology tests for the conditions studied (HIV, HBV, HDC, Chagas disease, strongyloidiasis, and schistosomiasis). In addition, other laboratory parameters will be included (hemogram, including haemoglobin, platelets, leucocytes, neutrophils, lymphocytes, and eosinophils, IgE, liver and renal function creatinine, urea, AST, ALT, GGT, bilirubin, coagulation...)
- 6. Diagnostic variables: Diagnoses of each disease/condition (HIV, HBV, HCV, Chagas disease, strongyloidiasis, schistosomiasis and female genital mutilation) based in ICD 10 codes registered by health professionals in the last 10 years including the intervention period.
- 7. Drug related to the diseases included in the study (e.g., ivermectine for strongyloidiasis) prescribed during the intervention period.
- 8. Co-morbidities: Other diseases diagnoses based on ICD-10 codes registered by health professionals into the system in the last 10 years including the intervention period. The aim is to study the possible association of other diseases (diseases associated with immunosuppression, mental health conditions, cardiovascular and other diseases, other infectious diseases...) with the studied diseases/conditions. In addition, to carry out the cost-effectiveness study (an economic analysis that will be essential to achieve the second objective of the study) all parameters must be considered to adjust the model, including the comorbidities of the diseases.
- 9. Immunosuppression status: Here it will include the prescription and billing of immunosuppressive drugs in the last 10 years including the intervention period as well as ICD-codes on transplant, haematological diseases, cancer and related diagnoses, and autoimmune diseases in the last 10 years for determination of immunosuppression status.
- 10. Minimum basic data set (CMBD) variables: hospitalization dates, primary diagnoses during hospitalizations, laboratory parameters during hospitalizations, drugs prescribed during hospitalization or outpatient units, cost associated or attributed to hospitalization, number of visits in outpatient units

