12. SUPPLEMENTARY FILES

Annex 1. Screening recommendations for infectious diseases and FGM targeting the migrant population residing in Catalonia, Spain.

- 1. Población diana: Se ha definido como población diana del estudio a inmigrantes que procedan de países en África, Latino América, Asia y Europa del Este. Se utilizó la división geográfica de la Comisión de Estadística de las Naciones Unidas.
- 2. Virus de la inmunodeficiencia humana (VIH): Todas las personas deberían tener acceso a una prueba de VIH si lo solicitan, pero además se recomienda ofrecer el cribado a la población inmigrante procedente de áreas dónde la prevalencia de VIH es >1% si no se ha hecho una prueba de VIH con anterioridad.
- **3. Otras infecciones de transmisión sexual (ITS):** Se recomienda pedir pruebas para sífilis y otras ITS basado en factores de riesgo. Por lo tanto, no se recomienda el cribado sistemático de sífilis y otras ITS ya que no hay evidencia del riesgo de exposición de una persona basándose en las variables: país de origen, edad y sexo.
- **4. Virus de la hepatitis B (VHB)**: Se recomienda realizar el cribado de VHB mediante la detección del antígeno australiano (HBsAg) y el anticuerpo contra el antígeno core (anti-HBc) a todos los inmigrantes procedentes de un área con prevalencia intermedia o alta de VHB (≥2%). *Además, se ofrecerá cribado de VHB a inmigrantes procedentes de Marruecos y Guinea Ecuatorial, aunque la prevalencia en estos países es <2%.

Se ofrecerá pauta vacunal a las personas con un test serológico negativo.

- **5. Virus de la hepatitis C (VHC):** Se recomienda realizar cribado de hepatitis C mediante el anticuerpo anti-VHC a todos los inmigrantes procedentes de áreas con una prevalencia de VHC ≥2%.
- **6. Tuberculosis (TB) activa:** Se recomienda el cribado de TB activa utilizando radiografía de tórax a inmigrantes recién llegados (<5 años) procedentes de países con una incidencia >50 casos/100.000 habitantes. Si la persona tiene una radiografía previa, se debe valorar la situación antes de solicitar otra radiografía de tórax.

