2.3 Endpoints

Primary Endpoints

Endpoint 1: For the detection rate of all aggregated infections, the monthly detection rate based on positive serologies, chest radiographies, the International Classification of Diseases Ninth Revision (ICD-9 for Andalusia) or Tenth Revision (ICD-10 for Catalonia) of FGM and/or gynaecologist referrals will be considered within the migrant patients who visited their assigned centre during the intervention period. Also, positive tuberculin skin test (TST) and/or Interferon Gamma Release Assay (IGRA) and stool samples will be considered for the Andalusian site. Control and intervention PCCs will be compared before and after the implementation.

Secondary Endpoints

Endpoint 2: For the detection rate of each individual condition, the infections and FGM, the monthly detection rate based on positive serologies, chest radiographies, ICD-9/ICD-10 of FGM and/or gynaecologist referrals, TST/IGRA and stool samples (for Andalusia) will be considered within the migrant patients who visited their assigned centre during the intervention period. Control and intervention PCCs will be compared before and after the implementation.

Endpoint 3: The number of early diagnoses of HIV will be assessed using the CD4 cell count of migrant patients diagnosed with an HIV infection, and will be compared between the control

and intervention PCCs before and after the implementation. If possible, we will estimate the monthly detection rate of early HIV diagnoses and also compare it between the intervention and control PCCs.

Endpoint 4: The number of early diagnoses of HBV and HCV will be assessed using the levels of transaminases, platelets, bilirubin, and clotting parameters from blood analyses of migrant patients diagnosed with HBV or HCV, and will be compared between the control and intervention PCCs before and after the implementation. If possible, we will estimate the monthly detection rate of individuals diagnosed with HBV or HCV presenting high levels of transaminases, platelets, bilirubin, and clotting parameters and also compare it between the intervention and control PCCs.

Endpoint 5: The number of the screening tests performed of all aggregated infections (serological tests, chest radiographies, TST or IGRA tests and stool samples in the case of the Andalusian site) will be compared between the intervention and control PCCs before and after the implementation.

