Endpoint 6: The number of the screening tests performed for each individual condition will be compared between the intervention and control PCCs before and after the implementation.

Endpoint 7: Associations between the screening performance of the aggregated infections with different socio-demographic and epidemiological factors, such as, sex, age, geographic areas immunosuppression status, being attended in an intervention centre, fulfilling the screening criteria, among others, will be analysed.

Endpoint 8: Associations between the screening performance of each individual condition with different socio-demographic and epidemiological factors, such as, sex, age, geographic areas immunosuppression status, being attended in an intervention centre, fulfilling the screening criteria, among others, will be analysed.

Exploratory Endpoints

Endpoint 9: The number of migrant patients under follow-up in the hospital after a diagnosis of an infection or FGM will be estimated using the Minimum basic dataset (MBDS).

Endpoint 10: The number of migrant patients under treatment after a diagnosis will be estimated using the data from the EPR systems and MBDS.

Endpoint 11: The prevalence of each condition will be estimated using as the denominator the total number of tested migrant patients for that specific condition.

3. Study Methods

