intervention level. Linear regressions will be performed for the monthly detection rates of the aggregated infections, and of each individual condition, comparing the intervention and control centres before and during the intervention period.

- Other secondary outcomes will be the proportion of screening tests performed for the aggregated infections and for each individual condition, and factors associated with having a higher screening performance. For this, associations with continuous variables will be evaluated using t-tests, or one-way analysis of variance (one-way ANOVA) for normally distributed quantitative variables, while for not normally distributed quantitative variables, Wilcoxon Rank-Sum and Kruskal-Wallis tests will be carried out. Pearson's chi-square test or Fisher's exact test will be performed to evaluate the associations between categorical variables. In addition, odds ratio (OR) will be estimated (Table 3). Mixed effects logistic regression models will be carried out to identify associations between the screening performance and socio-demographic and epidemiological characteristics, and adjusted odds ratio (aOR) will be estimated, using the region of the PCC as a random intercept (Table 3).
- **b.** The **prevalence** of each individual condition will be estimated and reported with its respective 95%CI. The prevalence for each infection was defined as the number of diagnoses identified by the screening tests performed among the people that were tested. Serology tests will be contemplated for HIV, HBV, HCV, *T.cruzi*, *S.stercoralis* and *Schistosoma spp.* infections; for active TB, chest radiographies will be examined; for FGM, the completed questionnaires and/or referrals to specialists will be considered.

See table 4 for details of the methodology employed for the outcomes.

Data analysis in Andalusia

A similar analysis approach will be carried out in Andalusia but the limited number of PCCs may prevent to estimate the health impact of the tool, therefore, we plan to estimate preliminary effectiveness data. In addition, the analysis for syphilis, latent TB and intestinal parasites will be executed. Nevertheless, because the pilot study will be conducted in six PCCs of one area (Almería), we won't be able to carry mixed-effects logistic regression models and instead, multiple logistic regressions will be performed.

7. Tables and Figures

Table 1. Description of the ISMiHealth sample.

| Variables | Summary statistics | | |

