|---------------------------------|---------------------------------|----------------|----------|-----------------|----------|
| Centre | | | | | |
| Type of centre (urban or rural) | | | | | |
| Index of socioeconomic | | | | | |
| deprivation (MEDEA index) | | | | | |
| Arm of the intervention | | | | | |
| Patient | | | | | |
| Sex | | | | | |
| Age | | | | | |
| Area of birth^ | | | | | |
| Assigned PCT | | | | | |

| Referrals to specialists | | | |
|-----------------------------------|--|---|--|
| Drugs prescribed during the | | | |
| intervention | | | |
| Other diagnoses | | | |
| Immunosuppression status | | | |
| Migrants with screening criteria | | | |
| for XX^ | | | |
| CD4 cell count, viral load and/or | | | |
| laboratory parameters* | | | |
| Hospitalisation | | | |
| Follow-up visits after | | | |
| hospitalisation | | | |
| Mortality | | _ | |

PCT: primary care team, XX: aggregated infections or any of the conditions, OR: odds ratio, aOR: adjusted odds ratio, CI: confidence interval; Region will be used as a random intercept for the logistic regressions; ^Only one of these variables will be added to the multiple logistic regression model due to highly correlation; *When applicable

Table 4. Description of the methodology employed for each outcome

| Outcome | | Methodology |
|--|---------------------------------|------------------------------------|
| Detection rate of all aggre | gated infections | Difference in differences analysis |
| | HIV cases | |
| | Syphilis cases^ | |
| | HBV cases | |
| Detection rate of each | HCV cases | Difference in differences |
| individual condition | active TB cases | analysis |
| | latent TB cases^ | |
| | T.cruzi infection cases | |
| | S.stercoralis infection cases | |
| | Schistosoma spp. infection | |
| | cases | |
| | Intestinal parasites cases^ | |
| | FGM cases | |
| Early diagnoses of | HIV | Bivariate analysis and, if |
| infections | HBV | possible, difference in |
| | HCV | differences analysis |
| Screening tests performed of all aggregated infections | | Bivariate analysis |
| | HIV | |
| | Syphilis^ | |
| | HBV | |
| Screening tests | HCV | |
| performed for each | active TB (chest radiographies) | Bivariate analysis |
| individual condition | latent TB^ (TST/IGRA) | |
| | T.cruzi infections | |
| | S.stercoralis infections | |
| | Schistosoma spp. infections | |

| | Intestinal parasites^ | |
|----------------------------|-----------------------------|--------------------------------|

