| alert_fgm | Patients fulfilling the criteria for the screening of FGM | Qualitative | Yes/No |
| sero_hiv | Serologies for HIV | Qualitative | Yes/No |
| sero_syph^ | Serologies for syphilis | Qualitative | Yes/No |
| sero_hbv | Serologies for HBV | Qualitative | Yes/No |
| sero_hcv | Serologies for HCV | Qualitative | Yes/No |
| cxray | Chest radiographies for active TB | Qualitative | Yes/No |
| tst^ | TST for latent TB | Qualitative | Yes/No |
| igra^ | IGRA for latent TB | Qualitative | Yes/No |
| sero_chagas | Serologies for T.cruzi infection | Qualitative | Yes/No |
| sero_strongy | Serologies for S.stercoralis infection | Qualitative | Yes/No |
| sero_schisto | Serologies for Schistosoma spp. infection | Qualitative | Yes/No |
| stool_intpar^ | Stool samples for intestinal parasites | Qualitative | Yes/No |
| fgm | Questionnaires completed for FGM | Qualitative | Yes/No |
| dx_hiv | Diagnosis of HIV | Qualitative | Yes/No |
| cd4 | CD4 cell count | Quantitative | |
| hiv_vl | HIV viral load | Quantitative | |
| dx_syph^ | Diagnosis of syphilis | Qualitative | Yes/No |
| dx_std | Diagnosis of other sexually transmitted diseases (STDs) | Qualitative | Yes/No |
| dx_hbv | Diagnosis of HBV | Qualitative | Yes/No |
| dx_hcv | Diagnosis of HCV | Qualitative | Yes/No |
| dx_activetb | Diagnosis of active TB | Qualitative | Yes/No |
| dx_latenttb^ | Diagnosis of latent TB | Qualitative | Yes/No |
| dx_chagas | Diagnosis of T.cruzi infection | Qualitative | Yes/No |
| dx_strongy | Diagnosis of S.stercoralis infection | Qualitative | Yes/No |

| dx_schisto | Diagnosis of Schistosoma spp. infection | Qualitative | Yes/No |
|-----------------|--|--------------|---|
| dx_intpar^ | Diagnosis of intestinal parasites | Qualitative | Yes/No |
| dx_fgm | Diagnosis of FGM cases | Qualitative | Yes/No |
| referral | Referral to specialists due to a diagnosis during the intervention | Qualitative | Yes/No |
| other_dx | Other diagnoses made during the intervention (besides from the infections included in the study and FGM) | Qualitative | ICD-9 or ICD-10 |
| com_dx | Comorbidities | Qualitative | ICD-9 or ICD-10 |
| immune_dx | Immunosuppressive diagnoses during the intervention period | Qualitative | ICD-9 or ICD-10 |
| drugs | Drugs prescribed to patients during the intervention | Qualitative | Anatomical Therapeutic Chemical (ACT) codes |

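### Chest films count as active-TB screening tests, but nothing in the planned extraction separates them from films taken for other illnesses

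*SAP*

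**What the plan says.** - **Counts of tests.** SAP section 2.3, Endpoint 5, compares arms before and after implementation on "The number of the screening tests performed of all aggregated infections (serological tests, chest radiographies, TST or IGRA tests and stool samples" (part of that list applies to Andalusia only). For Endpoint 6, "The number of the screening tests performed for each individual condition will be compared between the intervention and control PCCs". SAP section 7, Table 4, names the chest radiograph as the active-TB test and assigns bivariate analysis.
- **Associations.** Endpoint 8 relates having each test to arm and other factors. Table 3 reports odds ratios and adjusted odds ratios.
- **Prevalence.** Endpoint 11 is calculated "using as the denominator the total number of tested migrant patients for that specific condition". SAP section 6, part b, adds "for active TB, chest radiographies will be examined".
- **Data field.** SAP Annex 1 defines cxray as "Chest radiographies for active TB", with values yes or no. Protocol section 7, variable group 5, lists "X-rays, serological or microbiology tests for the conditions studied". Neither list contains a request reason.
- **Population and source.** SAP section 3.2 takes in migrants whatever the reason for their visit, and section 3.4 sets a retrospective extraction. The five-year residence limit in section 3.2 is attached to the TB recommendation, not to the test count. Annex 1 has an eligibility flag, alert_activetb, but Endpoints 5, 6 and 11 are not restricted to it.

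**The concern.** A serology for HIV or *T. cruzi* shows by its nature which infection was looked for. A chest film does not, because the same entry in the record can come from cough, pneumonia, heart disease or injury. The plan states a purpose for the counted films but no means of recognising it. An analyst who receives a yes/no field after the intervention year cannot recover that information.

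At stake is whether the TB part of the screening endpoints measures TB screening or a mixture of screening and general radiography. Restricting to TB-eligible patients would reduce the problem but not remove it, since eligible people also have films for other reasons. The point concerns which films count as tests, not which count as detections.

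**Working it through.** **The plan's own figure.** There is none to reproduce. SAP section 4 sizes the study for the aggregated detection rate; no document gives a number of chest films or an expected screening uptake. All rates below are assumptions.

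**Model.** Let u be the share of TB-eligible people with a TB-screening film and o the share with a film for another reason, independent of u. The recorded yes/no share is

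p = 1 − (1 − u)(1 − o).

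**1. Ratios, equal background in both arms.** Take u = 5% in control and 15% in intervention centres. The true ratio is 0.15/0.05 = 3.0 and the true OR is (0.15/0.85)/(0.05/0.95) = 3.35.

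| o | p control | p intervention | Ratio | OR | Difference, points |
|---|---|---|---|---|---|
| 0% | 0.050 | 0.150 | 3.00 | 3.35 | 10.0 |
| 2% | 0.069 | 0.167 | 2.42 | 2.71 | 9.8 |
| 6% | 0.107 | 0.201 | 1.88 | 2.10 | 9.4 |
| 10% | 0.145 | 0.235 | 1.62 | 1.81 | 9.0 |

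If non-eligible patients are counted too and only 10% of migrants are eligible, u is replaced by 0.1u. The ratio then falls to 0.0347/0.0249 = 1.39, 0.0741/0.0647 = 1.15 and 0.1135/0.1045 = 1.09.

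**2. Differences.** The yes/no difference is (1 − o)(u₁ − u₀), so it shrinks only by the factor (1 − o), as the last column shows. If films rather than people are counted, the difference does not shrink at all. Per 1,000 eligible people at o = 6%, it is (150 + 60) − (50 + 60) = 100, the same as without background films. What is lost is precision: with Poisson counts and no clustering, the standard error rises from √(150 + 50) = 14.1 to √(210 + 110) = 17.9.

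**3. Unequal background.** With u = 2% v 6%, the true difference is 4.0 points.
- Background 5% control, 6% intervention: (1 − 0.94 × 0.94) − (1 − 0.98 × 0.95) = 0.1164 − 0.0690, or 4.7 points.
- Background 6% control, 5% intervention: (1 − 0.94 × 0.95) − (1 − 0.98 × 0.94) = 0.1070 − 0.0788, or 2.8 points.

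**4. Aggregated Endpoint 5.** Suppose 100 v 150 tests of all kinds per 1,000, a ratio of 1.50. Adding 50 background films to each arm gives 200/150 = 1.33; adding 20 gives 170/120 = 1.42.

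**5. Endpoint 11.** Take 20 screening films with 0.5% TB (0.1 case) and 50 background films. If the background films contain no TB, prevalence reads 0.1/70 = 0.14%. If they contain 1% TB, it reads 0.6/70 = 0.86%. The error can go either way.

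**The case against.** The strongest reply is that Annex 1 restricts the field to films for active TB, so on a literal reading a film after a fall is not counted. That is right as to intent, and it would be wrong to say that the plan sets out to count every film. But a label does not tell the data manager how to select the films, and no listed variable would let anyone check the selection.

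A reader might go further and infer that films for other illnesses swamp the TB count and shrink the apparent effect of the tool. The documents do not support that. They give no film volumes, so how far background films outnumber screening films is unknown. Shrinkage applies to ratios under equal background; count differences are not shrunk, and unequal background can enlarge the effect.

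A reader might also infer that TB prevalence is understated more in control centres. SAP section 2.2 estimates prevalence in the migrant population with no comparison by arm, and films taken for symptoms may hold more TB, not less.

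Protocol Annex 1, item 6 ("Si la persona tiene una radiografía previa, se debe valorar la situación antes de solicitar otra radiografía de tórax") is at most a sign that earlier films are expected. It guides ordering and says nothing about counting.

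Nor do other parts of the plan supply the missing rule. The case definitions in Protocol section 7 classify cases, not tests. In Table 3 the eligibility flag is an optional covariate, not a filter. Table 4 assigns the screening counts to bivariate analysis, not difference in differences, so stable centre differences in general radiography are not assured of being removed.

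**Conclusion.** The concern holds as a gap in definition: the plan names a purpose for the counted films but gives no operational rule for identifying them, and the planned extraction could not supply one later. With equal background films, the odds ratios for TB screening are attenuated. Under the assumed 5% v 15% uptake, a ratio of 3.0 reads as 2.4, 1.9 or 1.6 at 2%, 6% or 10% background. Absolute differences are little changed in size but less precise. With unequal background the direction is open. Aggregated Endpoint 5 is diluted less, and the TB denominator of Endpoint 11 is mis-specified in an unknown direction.

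The sizes rest wholly on assumed rates and on independence between screening and other films. The primary endpoint's sample size is untouched; the affected endpoints are secondary (5, 6, 8) and exploratory (11). The change should be made because it is cheap before extraction and may be impossible afterwards.

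**What to change.** Before extraction, amend the SAP as follows.

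1. Add the request reason to the cxray extraction wherever the record system holds it. Count a film as a TB screening test if the reason is screening or TB.
2. Where no reason is recorded, count the film only in patients who meet the algorithm-derived TB criterion (alert_activetb). Derive that flag in the same way in control centres, which have no prompts, and in both periods. State that it is imperfect, since Protocol section 7 (study limitations) says arrival date is not routinely collected.
3. Do not exclude films by respiratory, cardiac or trauma code in the main analysis. Prompts appear at visits for any reason, so such a rule could remove more true screening films from intervention centres. Use it only as a sensitivity analysis.
4. Report all-films counts, and Endpoint 5 with and without chest films, as sensitivity analyses.
5. For Andalusia, reconcile the Mantoux-first pathway in Protocol Annex 2, item 6, with Protocol section 6 and SAP Table 4, which treat the film as the active-TB test.

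The cost is a few lines of SAP text and one extra field, if the two record systems hold it; the documents do not say whether they do. The downside is that some true screening films will be missed or misclassified.

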consequently increasing the cost for health systems. Although migrant screening guidelines are becoming increasingly available, most of the screening strategies designed require the health professionals' active commitment to navigate much deeper into the guidance until finding the epidemiological information on the country of origin that is needed for the individual-based risk assessment to take the appropriate screening decision. In many cases, guidelines do not provide specific information by country of origin and a general recommendation is provided considering all migrants as a homogeneous group. Therefore, in many settings, the screening programme is overestimating the population at risk, thereby wasting the scarce health resources of the health system - for example, low prevalence of HBV and HCV in most Latin American countries would not justify screening of these infections to migrants coming from these countries.

With the aim of improving patient care by strengthening medical decisions, there has been an outstanding development of clinical decision support systems in the last decade²⁶. In such tools, the characteristics of an individual patient are matched to a computerized clinical staff knowledge base in patient-specific assessments and recommendations are then presented in electronic patient record (EPR) system to the clinical staff for decision. The decrease in consultation time, wrong diagnosis, and test duplication at primary care settings support the cost-effectiveness of implementing CDSS in screening²⁷.

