Health professionals from both intervention and control centres will receive training sessions, targeting staff of the centres including nurses, medical doctors, and other technicians. The sessions will cover background information on each infection, including epidemiology, diagnostic tools, treatment available, particular aspects in high-risk groups such as immunosuppressed patients, data on cost-effectiveness, and screening recommendations for migrants.

Participants' selection

Therefore, when an individual comes to the PCC for any reason, the health professional will receive a message, in the EPR system, inserted as a pending task assignment with a recommendation on the diseases that should be considered for screening, based on this person's background characteristics. The tool is also able to identify if a person had already a diagnosis of any of the conditions included in the algorithm (based on ICD-10, International Classification Diagnosis codes) or if a diagnostic test had been performed for any condition included in the program. In such cases, the automated electronic prompt does not appear for that condition. A pilot test will be conducted with 3 health professionals to assure the correct functioning of the tool. In the control centres, we will hold just training sessions with the same screening recommendations as for the intervention centres but will not initiate the tool/prompts onto the EPR system. When the patient comes to the PCC, health professionals will decide what diseases/conditions should be screened for according to the information received either through the digital software (intervention centres) or based on their knowledge on the epidemiological background of the diseases (control centres), which was included in the training programme. In any case, health professionals will be responsible for requesting a blood test or a chest radiography and/or the derivation to a specialist.

Participant's selection for the feasibility and acceptability evaluation (focus group discussions, IDIs and survey)

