| age | Age of the patient | Quantitative | From 14 years old in Andalusia and 15 |
| | | | years old in Catalonia with no age limit in |
| | | | both sites |
| area_birth | Area of birth of the patient | Qualitative | Africa/Latin-America/Asia/Eastern Europe |
| date_entry | Date of entry to the PCC | Quantitative | MM/DD/YYYY: Up to 12/31/2024 |
| date_exit | Date of exit to the PCC | Quantitative | MM/DD/YYYY: Up to 12/31/2024 |
| visits | Number of visits to the healthcare | Quantitative | |
| | centre | | |
| | | | |

| date_visits | Date of visits to the healthcare centre | Quantitative | MM/DD/YYYY: Up to 12/31/2024 |
|-----------------|---|--------------|------------------------------|
| lab_hgb | Haemoglobin | Quantitative | |
| lab_plt | Platelets | Quantitative | |
| lab_wbc | Leucocytes | Quantitative | |
| lab_neut | Neutrophils | Quantitative | |
| lab_lym | Lymphocytes | Quantitative | |
| lab_eos | Eosinophils | Quantitative | |
| lab_crea | Creatinine | Quantitative | |
| lab_urea | Urea | Quantitative | |
| lab_ast | Aspartate aminotransferase (AST) | Quantitative | |
| lab_alt | Alanine aminotransferase (ALT) | Quantitative | |
| lab_ggt | Gamma-glutamyl transpeptidase (GGT) | Quantitative | |
| lab_bili | Bilirubin | Quantitative | |
| lab_act | Coagulation | Quantitative | |
| alert_hiv | Patients fulfilling the criteria for the screening of HIV | Qualitative | Yes/No |
| alert_syph^ | Patients fulfilling the criteria for the screening of syphilis | Qualitative | Yes/No |
| alert_hbv | Patients fulfilling the criteria for the screening of HBV | Qualitative | Yes/No |
| alert_hcv | Patients fulfilling the criteria for the screening of HCV | Qualitative | Yes/No |
| alert_activetb | Patients fulfilling the criteria for the screening of active TB | Qualitative | Yes/No |
| alert_latenttb^ | Patients fulfilling the criteria for the screening of latent TB | Qualitative | Yes/No |
| alert_chagas | Patients fulfilling the criteria for the screening of T.cruzi infection | Qualitative | Yes/No |
| alert_strongy | Patients fulfilling the criteria for the screening of S. stercoralis infection | Qualitative | Yes/No |

| alert_schisto | Patients fulfilling the criteria for the screening of Schistosoma spp . infection | Qualitative | Yes/No |
|---------------|--|--------------|--------|
| alert_intpar^ | Patients fulfilling the criteria for the screening of intestinal parasites | Qualitative | Yes/No |

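### The screening-test endpoints do not separate patients who meet a condition's criteria from those who do not, so the tool's effect on its target patients is diluted and targeting is never compared by arm

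*SAP*

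**What the plan says.** SAP 2.3, Endpoint 6: "The number of the screening tests performed for each individual condition will be compared between the intervention and control PCCs", before and after implementation. Endpoint 5 uses the same measure in aggregate: "The number of the screening tests performed of all aggregated infections". SAP Table 4 assigns both a bivariate analysis only.

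SAP section 6 describes the outcome differently: "Other secondary outcomes will be the proportion of screening tests performed for the aggregated infections and for each individual condition". It names no denominator. The patient inclusion criteria in SAP 3.2 admit any migrant from the target regions, of the stated age, who is assigned to and attends a centre. They do not refer to meeting a condition's criteria.

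Endpoints 7 and 8 list eligibility as one factor among several: "being attended in an intervention centre, fulfilling the screening criteria, among others, will be analysed". In Table 3, area of birth and meeting the screening criteria carry the same mark, and the footnote says: "Only one of these variables will be added to the multiple logistic regression model due to highly correlation".

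The eligibility flags exist. SAP Annex 1 has one Yes/No variable per condition; for HIV it is defined as "Patients fulfilling the criteria for the screening of HIV". They are described in Table 1. No table crosses them with arm.

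**The concern.** SAP 3.1 and the Protocol's Aim 2 present the tool as an aid to targeted screening. The Protocol's justification faults guidance that treats migrants as one group, because "the screening programme is overestimating the population at risk, thereby wasting the scarce health resources of the health system". Control staff are trained on the same recommendations but get no prompt. How closely testing follows the criteria is therefore a main way in which the arms could differ.

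A plain test count gives the same credit to a test inside and a test outside the criteria. Two things follow. The effect in patients for whom a prompt can fire is averaged with patients for whom it cannot. And a rise confined to eligible patients cannot be told from a general rise in testing.

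There is also a timing question. Under Protocol section 5 the tool checks for an existing diagnosis or test: "In such cases, the automated electronic prompt does not appear for that condition". The HIV criterion in Protocol Annexes 1 and 2 itself requires no earlier HIV test. SAP 3.4 has all variables collected after the intervention year, and the flags in SAP Annex 1 carry no date. The SAP does not say at what moment eligibility is judged.

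**Working it through.** The plan gives no expected testing rate, eligible share or effect size for the screening-test endpoints, so there is no figure to reproduce. The 32-centre calculation in SAP section 4 concerns the primary detection rate. All rates below are assumptions.

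**Formula.** Let *e* be the share of visiting migrants who meet a condition's criteria. Pooled proportion tested = *e* × (rate in eligible) + (1 − *e*) × (rate in ineligible).

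**1. Dilution.** Control: 5% tested in both groups. Intervention: eligible 15%, ineligible unchanged at 5%. The true gain in eligible patients is 10 points.

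| *e* | Pooled control | Pooled intervention | Pooled gain |
|---|---|---|---|
| 0.1 | 5.0% | 0.1×15 + 0.9×5 = 6.0% | 1 point |
| 0.3 | 5.0% | 0.3×15 + 0.7×5 = 8.0% | 3 points |
| 0.5 | 5.0% | 0.5×15 + 0.5×5 = 10.0% | 5 points |
| 0.7 | 5.0% | 0.7×15 + 0.3×5 = 12.0% | 7 points |
| 1.0 | 5.0% | 15.0% | 10 points |

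The pooled gain is *e* times the gain in target patients.

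**2. Targeted and general rises look alike.** At *e* = 0.3, a rise to 8% in everyone pools to 0.3×8 + 0.7×8 = 8.0%, the same as the targeted rise above. In the general rise, 0.7×3 / 3.0 = 70% of the extra tests fall outside the criteria; in the targeted rise, none do.

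**3. What full masking would need.** A gain of *g* points in eligible patients is cancelled by a fall of *g* × *e*/(1 − *e*) points in ineligible patients. For example, at *e* = 0.3 with eligible 12% and ineligible 2%, the pooled rate is 0.3×12 + 0.7×2 = 5.0%, which reads as no effect. With the 10-point gain of step 1, the fall needed at *e* = 0.3 is 10×0.3/0.7 = 4.3 points. It would exceed the 5% available once *e* is above one third, since 10*e* = 5(1 − *e*) gives *e* = 1/3.

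**4. Does adjusting for eligibility repair it?** A logistic model with arm and eligibility as main effects was fitted to expected frequencies at *e* = 0.3, with control rates of 20% (eligible) and 10% (ineligible). The eligible-only odds ratio, 20% against 40%, is (0.40/0.60)/(0.20/0.80) = 2.67.

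- Intervention 40% and 10% (no change outside the criteria): pooled 13.0% against 19.0%, crude odds ratio 1.57, adjusted 1.62.
- Intervention 40% and 2% (off-criteria testing falls): pooled 13.0% against 13.4%, crude odds ratio 1.04, adjusted 1.04.

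Keeping eligibility as a main effect therefore recovers little or nothing. The contrast needs a split or an interaction with arm.

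**The case against.** The strongest reply is that the SAP leaves the denominator open and does not choose a pooled one. Section 6 speaks of a proportion, and the Protocol's list of study variables puts the number of migrants with screening criteria beside the number of tests. That is fair as to intent. But an eligible denominator is nowhere stated, and Endpoints 5 and 6 as written are counts with no split.

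Further points stand and limit the concern:

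- A reader might infer that a well-targeted tool could look ineffective or even harmful to testing. The documents describe prompts for conditions whose criteria are met. They describe no function that discourages other tests, and both arms are trained on the same recommendations. Dilution is the expected consequence; masking is conditional.
- A reader might infer that every test outside the criteria is waste. Protocol Annex 1 says anyone who asks should have access to an HIV test, and tests may also be ordered for symptoms or individual risk.
- A reader might infer that tested patients will be recoded as ineligible. The flag is defined as meeting the criteria, not as a prompt shown, and nothing says it is read at extraction. This is a risk from silence, not a stated rule.
- Endpoints 7 and 8 are partly covered: Table 3 gives tests performed and an unadjusted odds ratio by eligibility, though never by arm.
- In Andalusia the HIV, HCV and syphilis criteria cover the whole target population, so the split is largely moot there.
- The primary outcome is a detection rate and is not a test count.

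**Conclusion.** The concern holds for the secondary screening-test endpoints, chiefly Endpoint 6 and mainly in Catalonia. No analysis compares the arms within patients who meet a condition's criteria, and the one place where eligibility enters a model allows it to be left out.

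If testing outside the criteria is the same in both arms, the pooled gain is the eligible share times the gain in target patients: 3 points instead of 10 at an assumed 30% eligible. Whatever the rates, the planned analyses cannot show by arm whether testing became better targeted. A null or reversed result would need off-criteria testing to fall in the intervention arm as well as a low enough eligible share. The documents give no rates by which to judge that, so it should not be presented as the likely outcome.

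**What to change.** - **Endpoint 6.** Keep the total test count. Add, as the key comparison for each condition, the proportion tested by arm and period among visiting migrants who meet that condition's criteria (the alert variable). Report the same comparison in criteria-negative patients as testing outside the criteria, without calling it inappropriate.
- **Endpoint 8.** Keep the alert variable in the adjusted model whatever is decided about area of birth, and add an arm-by-eligibility term.
- **Endpoints 5 and 7.** A patient can meet one infection's criteria and not another's, so state the unit: either patient-condition pairs that meet the criteria, or patients who meet at least one infection's criteria.
- **The flag.** Ask the data managers to derive it identically in both arms and periods, from status before the patient's first visit in the period, not from prompts shown or status at extraction. This must happen before country is aggregated to region (Protocol section 9), because SAP Annex 1 holds only area of birth and undated Yes/No test and diagnosis fields. Add an 'unknown' category for active TB where arrival date is missing, which the Protocol's limitations section expects.
- **Andalusia.** State that the split is largely moot for HIV, HCV and syphilis.

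The cost is SAP wording, a small change to the extraction request and wider intervals for rare conditions. No screening criterion or clinical procedure changes.
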